6.0 Screening and Enrollment

6.1 Screening and Enrollment (P1)

Children with pneumonia presenting to the ED at Monroe Carell Jr. Children's Hospital at Vanderbilt or Children's Hospital of Pittsburgh will be potentially eligible for study. The pneumonia radiology alert tool will be used to identify potentially eligible children in a systematic and efficient manner using natural language processing (NLP). Those who screen positive according to the radiology NLP algorithm will trigger a Best Practice Alert (BPA) or similar within the EHR which queries the provider to confirm the diagnosis of pneumonia and assesses for study inclusion/exclusion criteria. In instances where a chest radiograph is not captured via the NLP algorithm (e.g. a radiograph obtained at an outside facility), an alternative pathway is available to trigger the subsequent BPAs leading to enrollment. Due to the nature of the research, we will seek a waiver of informed consent as has been done in similar pragmatic studies at our institutions.¹⁷⁻²¹ Thus, at this point, eligible children will be considered enrolled. During intervention periods, providers caring for enrolled children will be presented with a detailed decision support strategy that emphasizes management in accordance with national guideline recommendations. During control periods, no additional decision support will be provided.

6.2 Screening and Enrollment (P2)

Screening and enrollment procedures for P2 will be identical to P1. For children randomized to the intervention arm, providers will be presented with prognostic information regarding risk for severe disease outcomes via an EHR-based decision support strategy that emphasizes management in accordance with national guideline recommendations. During control periods, no additional decision support will be provided.

7.0 Study Procedures

7.1 EHR-based Antibiotic Decision Support (P1)

For enrolled subjects assigned to the decision support arm, providers will receive antibiotic recommendations in accordance with the 2011 PIDS/IDSA guideline, tailored to site of care and illness severity. For instance, in young children with mild illness being discharged from the ED, the support tool will offer guidance regarding when a strategy of watchful waiting might be favored over empiric amoxicillin (e.g., fully immunized toddler with upper respiratory tract symptoms). Similarly, in those being admitted to a general ward, the tool will advise consideration of oral therapy in children with good oral intake, or when to consider adjunctive therapy with a macrolide or anti-staphylococcal antibiotic. *Importantly, the tool will offer treatment recommendations only and will not proscribe a specific treatment plan.* If a provider chooses to prescribe therapy not in accordance with the national guideline, the tool will query providers regarding reasons for discrepant prescribing for later analysis.

7.2 Outcomes (P1)

The primary outcome is the proportion of children exclusively receiving guideline-concordant 1st line antibiotic therapy during the first 24 hours of care (Table 1). For patients discharged from the ED, this will include antibiotics received in the ED as well as antibiotic

Table 1. Concordant Use Definitions for 1st Line Antibiotics¹

Disposition	<6 Years of Age	≥6 Years of Age
Home care	No antibiotics or amoxicillin	Amoxicillin
Inpatient, ward	Ampicillin/amoxicillin	Ampicillin/amoxicillin
Inpatient, ICU or complicated disease ²	Ampicillin or ceftriaxone +/- anti-staphylococcal +/- macrolide	Ampicillin or ceftriaxone +/- anti-staphylococcal +/- macrolide

ICU, intensive care unit ¹Unless specific pathogen identified or known drug allergy ²eg, empyema

prescriptions provided at discharge. For hospitalized patients, this will include therapy received during the first 24 hours of care beginning with ED triage. A patient following treatment according to table 1 will be considered as concordant, whereas deviations from these treatments will be considered discordant.

Secondary outcomes include exclusive use of concordant antibiotic therapy for the entire episode, any use of concordant antibiotic therapy during the first 24 hours of care and for the entire episode, and ED revisits and hospitalizations within 72 hours and 7 days of the index discharge. Index visit is defined as the enrollment ED visit or hospitalization through discharge.

Exploratory outcomes include time to first antibiotic, lack of antibiotics during the first 24 hours of care and for the entire episode, and changes in antibiotics after 72 hours, and death, and for hospitalized children, delayed ICU transfer, defined as >24 hours following hospitalization.

7.3 Data Collection/Management (P1)

Data collection will be triggered by the pneumonia BPA and will be acquired directly from the EHR and stored securely for later analysis. Prior to study initiation, support analysts will conduct detailed

requirement explorations to identify necessary data elements and associated data flows, validate accuracy, and evaluate for missing data. Data to be collected includes decision support usage statistics, visit details (e.g., admission and discharge date and time, site of care, ED revisits or hospital readmissions), patient demographics (e.g., age, sex, race, insurance), medication orders and prescriptions (dose, frequency, route, and duration), laboratory testing and results, radiologic studies, and data elements from the decision support applications.

7.4 EHR-based Prognostic Decision Support (P2)

For enrolled subjects assigned to the decision support arm, providers will receive prognostic information derived using our previously validated and best performing model. The decision support application will automatically calculate predicted risk for moderate (intensive care) and severe (respiratory failure or shock) outcomes using the parameters derived from the prognostic tool’s regression equation. Outcome probabilities will be integrated into the decision support application and displayed within the EHR. The support application will also report any objective criteria necessitating hospitalization (e.g., hypoxia) or potential intensive care (e.g., hypotension, SpO₂<92% despite FiO₂≥ 50%) to further inform site of care decisions. The application will also query providers regarding factors influencing site of care decisions to inform analyses describing discrepancies between risk assessments and decision-making (e.g., hospitalization of low risk children) and provider variation in risk tolerance. *Importantly, the tool will offer prognostic information only and will not proscribe a specific site of care or management plan. All site of care decisions will remain at the discretion of the treating provider.*

Table 2. Appropriate Site of Care Definitions

Disposition	Appropriate if:
Home care	No subsequent hospitalization within 24h
Inpatient, ward	Hospital length of stay ≥ 24h; or hospital length of stay < 24h but objective criteria for admission present (eg, need for supplemental oxygen); and no subsequent transfer to ICU within 24h
Inpatient, ICU	ICU length of stay ≥ 24h; or ICU length of stay < 24h but objective criteria for ICU admission present (eg, respiratory failure)

h, hours; ICU, intensive care unit

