2.0 Rationale and Study Phases

Extensive variation in both antibiotic use and hospitalization decisions is evident among clinicians caring for children with pneumonia, with high potential for avoidable harm. In our prior study, one-third of children were hospitalized for less than 48 hours and nearly 10% less than 24 hours. Some of these hospitalizations were likely unnecessary. Most of these children also received broad-spectrum antibiotic therapy instead of the narrow-spectrum agents recommended by the national guideline. Conversely, one-third of children admitted to intensive care were initially managed on a general ward—earlier transfer for more intensive therapy may have improved outcomes for some of these children. New strategies to inform decision making are needed, and the combination of risk stratification using objective tools and clinical decision support in the ED setting are innovative and promising approaches to achieve this goal.

Phase 1: *To test the hypothesis that electronic antibiotic decision support increases guideline-concordant antibiotic use compared with usual care in the ED.*

The primary outcome is the proportion of children exclusively receiving guideline-concordant 1st line antibiotic therapy during the first 24 hours of care (Table 1). Secondary outcomes include exclusive use of concordant antibiotic therapy for the entire episode, any use of concordant antibiotic therapy during the first 24 hours of care and for the entire episode, and ED revisits and hospitalizations within 72 hours and 7 days of the index discharge.

Phase 2: *To test the hypothesis that the delivery of severity information generated by our prognostic tool leads to more appropriate site of care disposition compared to usual care.*

The primary outcome is appropriate site of care disposition (Table 2). Surveillance for subsequent ED visits and hospitalizations to our institutions as well as escalation to higher levels of care will be captured within the EHR data extracted by the decision support application. Secondary efficacy and safety outcomes include the overall site of care disposition (ED discharge, ward, ICU), and ED revisits and hospitalizations within 72 hours and 7 days of the index discharge.

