8.4 Power and Sample Size (P2)

As outlined in P1, we anticipate nearly 2000 children with pneumonia will be evaluated annually during the conduct of these studies. Assuming conservatively that data for 2000 children (1000 in each arm) are captured during the two-year study period, and 90% appropriate site of care disposition in the usual care arm (based on data from the EPIC cohort)²³, we will be able to detect an absolute difference of $\geq 3.4\%$ in appropriate care disposition at an alpha level of 0.05 with 80% power.

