8.6 Potential Limitations and Alternative Approaches (P2)

In contrast to our studies of antibiotic decision support, we chose to randomize at the individual level rather than monthly crossovers since potential for contamination effects is minimal (i.e. risk estimates are unique to each individual's set of circumstances and linked to a complex algebraic equation). Although we hypothesize that supplying providers with objective prognostic information will improve care decisions, this information could lead to unintended outcomes, such as increased hospitalizations in low risk children. This would be an important finding in itself, as it contrasts with prior studies in adults highlighting the usefulness of adult pneumonia severity tools, and provides valuable data regarding how risk information is interpreted and applied.

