### Appropriate Site of Care Definitions

Disposition	Appropriate if:
Home care	No subsequent hospitalization within 24h
Inpatient, ward	Hospital length of stay $\geq$ 24h; or hospital length of stay $<$ 24h but objective criteria for admission present (eg, need for supplemental oxygen); and no subsequent transfer to ICU within 24h
Inpatient, ICU	ICU length of stay $\geq$ 24h; or ICU length of stay $<$ 24h but objective criteria for ICU admission present (eg, respiratory failure)

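### The Phase 2 primary endpoint is largely insensitive to over-admission, and the SAP drops the secondary outcome that would show shifts in admission

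*Protocol*

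**What the plan says.** Table 2 in Protocol 7.4 defines appropriate site of care by disposition.

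- **Home:** appropriate unless the child is hospitalized within 24 h.
- **Ward:** the first route to appropriate is "Hospital length of stay ≥ 24h". A shorter stay qualifies only if objective admission criteria are present. A final clause adds that there must be no ICU transfer within 24 h.
- **ICU:** an ICU stay of 24 h or more qualifies; a shorter one needs objective ICU criteria.

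SAP Appendix 2 repeats the rule ("Hospital length of stay $\geq$ 24h"). Protocol 7.5 describes blinded adjudication for stays under 24 h. SAP 11.1 has a blinded investigator decide appropriateness more generally, but by the Appendix 2 table.

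The rationale (Protocol 2.0) reports that "one-third of children were hospitalized for less than 48 hours and nearly 10% less than 24 hours. Some of these hospitalizations were likely unnecessary". It also describes ICU children who were first managed on a ward. Protocol 8.6 warns that "this information could lead to unintended outcomes, such as increased hospitalizations in low risk children" and says that such a result would matter.

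Protocol 2.0 and 7.5 and SAP 6.1.2 list overall disposition (ED discharge, ward, ICU) as a secondary outcome. In SAP 3.2, 5.2 and 11.2, SO 1 is instead the proportion with appropriate site of care.

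**The concern.** Phase 2 asks whether severity information leads to more appropriate site of care. One of the two problems that motivate it is unnecessary short hospitalization, and the rationale's figures run to 48 h. Table 2 accepts every stay past 24 h as needed unless the ICU-transfer clause applies. A tool that safely keeps low-risk children at home can therefore show little on the primary when the avoided stays would have passed 24 h. A tool that adds such stays can look neutral.

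Length of stay is also settled after allocation, by providers who are not blinded (SAP 6.3.2). If the risk display led to earlier discharge of admitted children without objective criteria, their scores would fall although nobody's site of care had changed.

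The outcome that would show movement between home, ward and ICU is missing from the SAP's operative objectives, so the gap is not filled elsewhere among the analyses specified as secondary.

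**Working it through.** **1. The plan's own figure.** Protocol 8.4 assumes "data for 2000 children (1000 in each arm) are captured during the two-year study period" and a usual-care rate of 90%, and states a detectable difference of 3.4 points at alpha 0.05 and 80% power. Sidedness is not stated; two-sided is assumed here.

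Power = Φ[(d − 1.96·SE0)/SE1], with d = 0.034 and pooled rate 0.917:
- SE0 = √(2 × 0.917 × 0.083/1000) = 0.01234
- SE1 = √((0.90 × 0.10 + 0.934 × 0.066)/1000) = 0.01231
- Power = Φ[(0.034 − 0.02418)/0.01231] = Φ(0.797) = 78.7%

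The smallest increase detectable with 80% power is 3.45 points (3.44 by the arcsine formula). The stated figure reproduces. A decrease from 90% needs about 4.1 points.

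**2. Scores under Table 2 for a child without objective criteria.** No rates are needed for this step.

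| Course | Score |
|---|---|
| Home, not hospitalized within 24 h | 1 |
| Home, hospitalized within 24 h | 0 |
| Ward under 24 h | 0 |
| Ward 24 h or more, no ICU transfer within 24 h | 1 |
| Ward, hospital stay 24 h or more, ICU transfer within 24 h | 0 or 1, depending on how the clause is read |
| ICU under 24 h | 0 |
| ICU 24 h or more | 1 |

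- Home to ward of 24 h or more, or the reverse: change 0.
- Home to ward under 24 h: change −1. Avoiding that stay: +1.
- Ward stay shortened from 30 h to 20 h: change −1, same site of care.

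The fifth row is ambiguous because the punctuation of the ward rule allows two readings. If the ICU-transfer clause covers both ward branches, the score is 0. If it covers only the under-24 h branch, the score is 1.

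**3. Illustrative size.** Assumptions: 31% of enrolled children are admitted (median in Protocol 1.0, range 19-69%, from other hospitals), and stays are distributed as in the prior study (one-third under 48 h, 10% under 24 h).

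- Stays of 24-48 h: 0.31 × (0.333 − 0.10) = 7.2% of enrolled children (0.19: 4.4%; 0.69: 16.1%).
- Half of these sent home: 3.6% of the arm (2.2-8.0%). The primary changes by 0, or by −0.18 points if 5% of them are hospitalized within 24 h (0.036 × 0.05).
- Stays under 24 h: 0.31 × 0.10 = 3.1% (1.9-6.9%). This is the pool in which avoided over-admission can register. If all lacked criteria and all were avoided, the gain at 31% is 3.1 points (power 70%). If half lacked criteria, it is about 1.6 points (power 22%). At 69% admitted, the same two cases give 6.9 points (power above 99%) and 3.45 points (power 80%).

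**4. Illustrative harm.** Suppose 10 more children per 100 are admitted, all without objective criteria.

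| Share of added stays under 24 h | Change in primary | Power |
|---|---|---|
| 0% | 0 | none beyond alpha |
| 10% | −1.0 | 11% |
| 25% | −2.5 | 42% |
| 50% | −5.0 | 92% |

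The same shift tested on admission share (31% to 41%) has power above 99%.

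**5. Illustrative earlier discharge.** If 2% of the arm, without criteria, left before 24 h instead of after, the primary would fall 2.0 points (power 30%). At 4.1% of the arm, the power to show an apparent worsening is about 80%.

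**The case against.** The strongest defence is that the endpoint still responds to much of what matters. It moves when a stay under 24 h without criteria is added or avoided, and when a child sent home is hospitalized within 24 h. If the ICU-transfer clause covers both ward branches, it also moves with early escalation, and earlier ICU placement is one of the two problems in the rationale. The risks displayed are for intensive care and for respiratory failure or shock, which fits that aim. All of this stands. A reader might infer that the primary cannot register the tool's main benefit, or that it passes every stay of 24 h or more whatever the child's condition. The documents support neither: they do not rank the two aims, and the ICU-transfer clause may fail a longer ward stay.

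A second defence is that the trial looks elsewhere. It plans overall disposition as a secondary, length of stay as exploratory, interactions with predicted risk, and provider queries about admitting low-risk children. This stands for the protocol. In the SAP, however, SO 1 no longer carries overall disposition, and the interactions are specified for the primary comparison, so they share its insensitivity.

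Third, scoring every admission by objective criteria has its own faults. The criteria appear only as examples, a long stay may have an unlisted reason, and the application shows the criteria to providers in one arm. This stands, and it argues against replacing the primary.

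Finally, the sizes rest on background rates and assumed shifts. No passage says that the display shortens ward stays, and shortening costs a point only when criteria are absent. That also stands; the sizes are illustrations.

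**Conclusion.** The concern holds in limited form. For a child without objective criteria, adding or avoiding an admission of 24 h or more leaves the primary unchanged. The exceptions are hospitalization within 24 h of being sent home and, on one reading of the clause, ICU transfer from the ward within 24 h. Leaving before 24 h costs such a child the point with no change in site of care. These results follow from Table 2 alone and need no assumed rate.

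The size does need assumptions. With 31% admitted (19-69%) and the prior study's stay distribution, about 7% of enrolled children (4-16%) have stays of 24-48 h. Moving half of them home changes the primary by about 0, against a detectable difference of 3.4 points. The documents do not say how many of these stays were avoidable, only that some of the short ones probably were.

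The endpoint is therefore partly blind to over-admission. A neutral primary result would not show that avoidable hospitalization was unaffected. What makes this worth correcting is that the SAP's operative secondary objective repeats the primary and omits the disposition outcome that would reveal such shifts.

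**What to change.** Keep the primary endpoint, and make four changes.

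1. In SAP 3.2, 5.2 and 11.2, make SO 1 the protocol's overall disposition (ED discharge, ward, ICU) compared by arm.
2. Pre-specify a further secondary that does not depend on length of stay. Apply the plan's own objective criteria to every admitted child, keep the existing 24 h return and escalation conditions, and derive the criteria from EHR data in the same way in both arms.
3. State in SAP 11.1 that the primary alone does not support a conclusion about avoidable hospitalization.
4. In Table 2 and Appendix 2, reconcile whether the ICU-transfer clause covers both ward branches.

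The cost is an SAP revision, a clarification of Table 2, and modest programming or chart review. The source data are collected from the EHR in both arms, and blinded review of disposition is already planned. The sponsor must turn the example criteria into a list. The criteria score may misclassify longer stays with unlisted reasons, so it should be supportive only. The primary's power calculation does not change.

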7.5 Outcomes (P2)

The primary outcome is appropriate site of care disposition (Table 2). Surveillance for subsequent ED visits and hospitalizations to our institutions as well as escalation to higher levels of care will be captured within the EHR data extracted by the decision support application. To adjudicate the appropriateness of brief hospitalizations and ICU stays (<24 hours), an investigator in both Nashville and Pittsburgh will review all hospitalizations meeting these criteria, blinded to intervention assignment.

Secondary efficacy and safety outcomes include the overall site of care disposition (ED discharge, ward, ICU), and ED revisits and hospitalizations within 72 hours and 7 days of the index discharge.

Exploratory outcomes include death, and for those hospitalized at the index visit, hospital length of stay.

7.6 Data Collection/Management (P2)

See Section 7.3

8.0 Statistical Considerations

8.1 Power and Sample Size (P1)

Based on ED and hospitalization data from our hospitals during the conduct of the EPIC study, we anticipate nearly 2000 total children with pneumonia will be evaluated annually during the conduct of these studies. Assuming conservatively that data for 750 children are enrolled in each arm, and 30% guideline-concordant antibiotic use in the usual care arm (based on our prior study of antibiotic use in the EPIC cohort)²³, we will be able to detect an absolute difference of $\geq 6.8\%$ in guideline-concordant prescribing at an alpha level of 0.05 with 80% power. Effective sample size may be reduced due to the cluster randomized nature of the study (a conservative estimate for effective sample size would be around 500 children in each arm).

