3.0 Previous Studies

From 2010 to 2012, our research team at Vanderbilt collaborated with two other sites to conduct the Centers for Disease Control and Prevention (CDC) funded Etiology of Pneumonia in the Community (EPIC) Study, a prospective, population-based surveillance study of community-acquired pneumonia hospitalizations in children and adults.^{2,22} We enrolled >2600 children, making EPIC the largest prospective study of pneumonia hospitalizations ever conducted in US children. Over 70% of children enrolled in EPIC had a viral pathogen detected whereas bacterial pathogens were identified in only 15% of children. Nevertheless, nearly 90% of children received antibiotics. In most cases, antibiotic treatment was discordant with the national guideline and broad-spectrum antibiotic use was common.²³ We have also evaluated the impact of the 2011 PIDS/IDSA guideline on antibiotic selection for children with pneumonia enrolled in EPIC, demonstrating only a modest reduction in the use of broad-spectrum antibiotics following publication of the guideline. Guideline-concordant use of narrow-spectrum aminopenicillins remained <20% by the end of the study, indicating a clear opportunity for further improvement.²³

We also used data from the EPIC study to develop a prognostic tool for assessing pneumonia disease severity in children. Prognostic tools use statistical modeling to combine inputs, such as demographics, clinical variables, and results of diagnostic tests, to produce reliable and unbiased risk estimates for a specified outcome. For our prognostic tool, we focused on acute in-hospital outcomes, organized into an ordinal severity scale consisting of 3 levels: severe, moderate, and mild. Our modeling strategy, ordinal logistic regression, offers increased statistical power and precision compared to binary/multinomial logistic regression, and the resulting output allows one to simultaneously estimate probabilities for each level on the outcome scale or in combination (e.g., probability of moderate to severe and probability of severe outcomes). Predictor variables for our prognostic tool were selected a priori and also informed by clinical expertise and literature review. We focused on objectively defined variables with strong hypothesized associations with the outcome that could be rapidly ascertained at presentation in the

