An important consideration in our analysis is the possibility of contamination effects in the usual care arm related to changes in provider behavior due to past exposures and awareness of the intervention. Such contamination would be expected to bias toward the null hypothesis. We posit that such effects will be of minor concern since 1) guideline-concordant prescribing at our institutions remains low despite the presence of both national and local practice guidelines and order sets for several years; 2) the ED is a busy environment with many providers (e.g., 40+ ED faculty plus mid-level providers and fellows/residents at Vanderbilt alone), such that repeated exposure to the intervention by any one provider would be infrequent, particularly early during the study period and during times of low pneumonia prevalence; and 3) resident physicians, the providers responsible for the majority of order entry and thus directly exposed to the intervention, rotate on a monthly schedule and only work in the ED once each year. We have designed our randomization and monthly crossover periods around these important considerations. Nevertheless, we acknowledge the potential for contamination, and we will formally evaluate for such effects in a secondary analysis by modeling the monthly proportions of guideline-concordant prescribing in each arm over the duration of the study period. We will then compare prescribing trends in both arms with a historical trend estimated from monthly proportions of guideline-concordant prescribing in the year prior to study initiation. By comparing prescribing trends in each arm to this historical trend, we will estimate both the degree of potential contamination as well as the independent impact of the intervention.

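### Phase 1's 80% power for a 6.8-point difference assumes 750 independent children per arm and an underived 30% control rate; at the plan's own effective size of 500, power is about 63% and the detectable difference 8.4 points

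*Protocol*

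**What the plan says.** The Phase 1 power statement is in Protocol 8.1 and is repeated in SAP 6.2.1. Its sample size is given as "Assuming conservatively that data for 750 children are enrolled in each arm". Its control rate is "30% guideline-concordant antibiotic use in the usual care arm (based on our prior study of antibiotic use in the EPIC cohort", with protocol reference 23 as the source. From these it claims a detectable absolute difference of 6.8 points "at an alpha level of 0.05 with 80% power". The closing sentence concedes that clustering may shrink the effective sample: "a conservative estimate for effective sample size would be around 500 children in each arm". No power or detectable difference is attached to that number.

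Three other places bear on the control rate:

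- Protocol 3.0 describes EPIC as surveillance of pneumonia hospitalisations and cites the same reference 23 for this finding: "Guideline-concordant use of narrow-spectrum aminopenicillins remained <20% by the end of the study". The title of reference 23 also limits it to hospitalised children.
- Protocol 7.2 counts children sent home in the primary outcome: "For patients discharged from the ED, this will include antibiotics received in the ED as well as antibiotic" prescriptions given at discharge. Its Table 1 accepts no antibiotics for home-care children under 6, and ceftriaxone-based regimens in ICU or complicated disease.
- Protocol 8.2 plans a "historical trend estimated from monthly proportions of guideline-concordant prescribing in the year prior to study initiation".

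**The concern.** Two inputs to the only Phase 1 power statement do not match the trial as designed.

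The first is the sample size. The 6.8 points is calculated as if 1,500 children had been individually randomised, but hospitals switch arms month by month. The plan acknowledges the loss of information and puts a number on it, then leaves the detectable difference unchanged.

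The second is the control rate. The 30% is credited to a study of hospitalised children, and nothing in the documents carries it over to a population that includes children discharged from the ED, or to the table that scores the primary outcome.

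At stake is how the result is read. A null or small difference would be judged against a sensitivity of 6.8 points at 80% power, which the clustered design does not deliver if the plan's own effective size is right.

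**Working it through.** **Inputs.** From Protocol 8.1 and SAP 6.2.1: 750 per arm, control rate 30%, difference 6.8 points, alpha 0.05, power 80%, conservative effective size 500 per arm. From Protocol 3.0: under 20% aminopenicillin use in EPIC, taken here at its upper limit of 20%. Control rates of 40-50% are my assumption, because the documents give no concordance rate for all ED children. Alpha is taken as two-sided. The plan does not say so, but two-sided reproduces its figure, whereas one-sided 0.05 would give 87.5% power and a detectable difference of 6.03 points.

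**Formula.** Two-proportion z test, pooled variance under the null, with p the mean of p1 and p2:

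z = [d·√n − 1.96·√(2p(1−p))] / √(p1(1−p1) + p2(1−p2)); power = Φ(z).

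**Step 1: the plan's own figure.** p1 = 0.300, p2 = 0.368, p = 0.334.

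- √(2 × 0.334 × 0.666) = 0.6670; × 1.96 = 1.307
- √(0.2100 + 0.2326) = 0.6653
- n = 750: 0.068 × 27.386 = 1.862; z = (1.862 − 1.307)/0.6653 = 0.834; power 79.8%

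Solving for 80% power gives 6.82 points. The stated 6.8 is therefore correct for 750 independent children per arm and contains no allowance for clustering.

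**Step 2: the plan's effective size.** Same rates, n = 500: 0.068 × 22.361 = 1.521; z = (1.521 − 1.307)/0.6653 = 0.320; power 62.6%. The detectable difference at 80% power is 8.40 points. Going from 750 to 500 corresponds to a design effect of 750/500 = 1.5.

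**Step 3: vary the control rate.**

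| Control rate | Power for 6.8 points, 750/arm | Detectable, 750/arm | Power for 6.8 points, 500/arm | Detectable, 500/arm |
|---|---|---|---|---|
| 20% | 87.6% | 6.1 | 72.0% | 7.5 |
| 30% | 79.8% | 6.8 | 62.6% | 8.4 |
| 40% (assumed) | 75.8% | 7.2 | 58.3% | 8.8 |
| 50% (assumed) | 75.2% | 7.2 | 57.8% | 8.8 |

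The least favourable rate examined was 45%: 75.1% power and 7.23 points at 750, 57.6% and 8.85 points at 500.

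**Step 4: which input matters more.** At 750 per arm, a control rate above 30% costs at most 79.8 − 75.1 = 4.7 points of power. At a 30% control rate, moving to 500 per arm costs 79.8 − 62.6 = 17.2 points. A lower control rate does not remove the shortfall: at 500 per arm, power for 6.8 points is 72.0% at a 20% control rate and still 79.3% at 15%.

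**The case against.** The strongest reply is that the plan hides nothing. It names the effective size of 500, calls it conservative, and also calls 750 enrolled a conservative figure. If clustering is milder or enrolment larger, power lies above 63%. That is fair, and it means 62.6% is the plan's cautious case, not a forecast. But a reader given 500 without its consequence will still carry away 6.8 points at 80%.

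On the control rate, a reader might infer that 30% is contradicted by the figure below 20% from the same reference. The documents do not establish that. The lower figure counts one drug class, while Table 1 also accepts ceftriaxone regimens in ICU or complicated disease and makes exceptions for allergy or an identified pathogen. One study could support both numbers. The two measures do come close for ward patients, where Table 1 lists only ampicillin or amoxicillin, so a sentence of derivation is still owed. Direction matters too: at 20% the power for 6.8 points would be higher, so against that figure 30% is the cautious choice.

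A reader might also infer that usual-care concordance has since risen to 40-50%. No passage gives such a rate, and Protocol 8.2 says concordant prescribing at these hospitals remains low despite guidelines and order sets. Those rows only bound the loss.

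**Conclusion.** The point holds as an incomplete power statement, not as an arithmetic error. The 6.8 points follows from its stated inputs. What the plan omits is the figure at its own conservative effective size: about 63% power for 6.8 points, or 8.4 points detectable at 80% power, with a 30% control rate. The missing derivation of 30% for all enrolled ED children is real but secondary, since it moves the 750-per-arm detectable difference only between 6.1 and 7.2 points over control rates of 20-50%.

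These figures assume a two-sided 0.05 test, no covariate gain, and 500 taken at face value as the number of independent children per arm. They do not support the stronger inference that the control-rate source makes the trial underpowered.

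**What to change.** In Protocol 8.1 and SAP 6.2.1:

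1. Put the detectable differences at 80% power side by side for control rates of 20%, 30% and an assumed 40-50%: 6.1, 6.8 and 7.2 points at 750 per arm; 7.5, 8.4 and about 8.8 points at an effective 500. State that the test is two-sided and that the 750 row ignores clustering.
2. Say that 30% is a planning assumption for the concordance outcome in all enrolled ED children, or check it against the pre-study-year concordance data planned in Protocol 8.2, covering all dispositions and scored with the table used for the primary outcome.
3. Do not replace 30% with the aminopenicillin-only figure below 20%, which is a different measure. Leave enrolment as it is.

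The cost of items 1 and 3 is a few sentences and a small table. The optional check in item 2 takes more work, because scoring by SAP Appendix 1 needs allergy, prior beta-lactam, effusion, severity and aspiration status for historical patients, and SAP 10.1 describes the outcome as captured by chart review. The downside is a less favourable stated detectable difference.
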